2 SCHEDULE OF ACTIVITIES

The Schedule of Activities (SOA) for the screening and initial on-treatment study period is provided in [Table 2-1](#). The SOA for the on-treatment period beyond Week 52 is provided in [Table 2-2](#).

Table 2-1: Schedule of Activities for Year 1 (IM047029)

Procedure	Screening (Days -28 to -1)	Week 0 (Day 1)	Week 4 (Day 28)	Week 12 (Day 84)	Week 26 (Day 182)	Week 52 (Day 365)	Unscheduled ^a	Notes
Visit Window (± n Days)			7	7	7	14		
Eligibility Assessments								
Informed Consent	X							See APPENDIX 2
Obtain Participant Number	X							
Medical History	X							
UC Disease History	X							
Prior Medications	X	X						
Concomitant Medications	X	X	X	X	X	X		Assessments after screening for change in concomitant medications (see Section 7.7)
UC Medications	X	X	X	X	X	X		
Tobacco / e-cigarette Use	X	X	X	X	X	X		Assessments after screening for change in use
Review Eligibility Criteria	X							See Section 6 for details
Physical Examination								See Section 9.5.1 for details
Weight	X	X		X	X	X		
Height	X							
Vital Signs (HR, BP, Temperature [°C])	X	X	X	X	X	X		
Complete Physical Examination	X			X	X	X		

Table 2-1: Schedule of Activities for Year 1 (IM047029)

Procedure	Screening (Days -28 to -1)	Week 0 (Day 1)	Week 4 (Day 28)	Week 12 (Day 84)	Week 26 (Day 182)	Week 52 (Day 365)	Unscheduled ^a	Notes
Visit Window (± n Days)			7	7	7	14		
Interim Physical Examination		X	X					
Additional Screening Tests								
12-lead ECG	X							See Section 9.5.3 for details
Examination of Ocular Fundus and Pulmonary Function ^b	X							
Cardiologist Clearance or 6-hour First Dose Observation ^c	X	X						
Electronic Diary (eCOA)								
Dispense and Train Participant on Electronic Daily Diary	X							
Demographics and Subject Characteristics		X						
Site Review of Electronic Daily Diary Compliance		X	X	X	X	X	X	
Blood and Urine Tests^d								See Section 9.5.4 for details
CBC and Differential Count	X	X	X	X	X	X	X	Blood test results from anytime within 30 days prior to starting first

Table 2-1: Schedule of Activities for Year 1 (IM047029)

Procedure	Screening (Days -28 to -1)	Week 0 (Day 1)	Week 4 (Day 28)	Week 12 (Day 84)	Week 26 (Day 182)	Week 52 (Day 365)	Unscheduled ^a	Notes
Visit Window (± n Days)			7	7	7	14		
Biochemistry ^d	X	X	X	X	X	X	X	dose of study intervention can be considered for screening process. Results must be documented, if obtained locally.
Varicella IgG	X							
Pregnancy Test - Serum or Urine beta-hCG ^e	X	X						See footnotes

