AE Reporting								
Monitor AEs		X	X	X	X	X	X	
Monitor SAEs	X	X	X	X	X	X	X	
COVID AEs	X	X	X	X	X	X	X	
IP Supply								
Dispense IP		X ^p	X	X	X	X	X	
Review Participant Compliance with IP			X	X	X	X	X	

AE, adverse event; BP, blood pressure; beta-hCG, beta-subunit of human chorionic gonadotropin; CBC, complete blood count; COVID, coronavirus disease; ECG, electrocardiogram; eCOA, electronic clinical outcome assessment; EDC, electronic data capture; [REDACTED]

[REDACTED] FDO, first dose observation; FSH, follicle-stimulating hormone; Hb, hemoglobin; HR, heart rate; HRQOL, health-related quality of life; [REDACTED] IBDQ, Inflammatory Bowel Disease Questionnaire; IFN, interferon; IgG, immunoglobulin G; LFT, liver function test; PCR, polymerase chain reaction; PCR, polymerase chain reaction; PGA, Physician's Global Assessment; RB, rectal bleeding; SARS-CoV-2, severe acute respiratory syndrome coronavirus 2; SAE, serious adverse event; SF, stool frequency; TDM, therapeutic drug monitoring; [REDACTED] UC, ulcerative colitis; [REDACTED]

[REDACTED] WOCBP, women of childbearing potential; [REDACTED]

^a If required, an unscheduled visit can be planned anytime during the treatment period. Data regarding study procedures conducted at such unscheduled visits (eg, blood, stool, and urine tests; safety assessments) will be documented in the EDC tool.

^b Need for fundic examination and pulmonary function is dependent on specific risk factors outlined in the product label.

^c Need for 6-hour FDO is dependent on specific cardiac risk factors outlined in the product label. A cardiologist's opinion is required in the setting of history of cardiac arrest, cerebrovascular disease, uncontrolled hypertension, severe untreated sleep apnea, history of recurrent syncope or symptomatic bradycardia; pre-existing significant QT interval prolongation (QTc greater than 500 msec) or other risks for QT prolongation, and patients on medicinal products other than beta-blockers and calcium channel blockers that may potentiate bradycardia; patients on class Ia (eg, quinidine, disopyramide) or class III (eg, amiodarone, sotalol) antiarrhythmic medicinal products, which have been associated with cases of torsades de pointes in patients with bradycardia have not been studied with ozanimod.

^d Complete list of clinical safety laboratory assessments is provided in [Section 9.5.4](#).

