^e WOCBP only. Pregnancy test anytime within 7 days prior to day of study intervention initiation is permissible – if pregnancy test is done locally, it must be documented.

^f Optional test of FSH level may be used to exclude childbearing potential in peri-menopausal females.

^g For all biologics, the washout period is 8 weeks or 5 elimination half lives, which ever is shorter, but it may be waived with the demonstration of absent drug levels on TDM assay.

ⁱ Stool PCR panel may be performed as an alternative to stool culture if that is in routine clinical use at a site.

^j Endoscopy- and biopsy-related procedure details will be provided to the sites in a separate document/manual.

^k A brief description about additional efficacy assessments is provided in [Section 9.1](#).

^l Only for Cohort 1.

^m Only for Cohort 2.

ⁿ A brief description about HRQOL assessments is provided in [Section 9.1.2.2](#).

^o A brief description about healthcare resource utilization assessments is provided in [Section 9.10](#).

^p Ozanimod titration will occur during the first 7 days of study intervention exposure, per label ([Table 7.1-2](#)). Participants will receive a phone call on Day 5 (when titrating their dose from 0.23 mg to 0.46 mg) and again on Day 8 (when titrating their dose from 0.46 mg to 0.92 mg) as a reminder about the dose adjustment.

Table 2-2: Schedule of Activities for Year 2 (IM047029)

Procedure	Week 104 EOT/ET ^a (Day 728)	Week 116 PTFU (Day 812)	Unscheduled ^b	Notes
Visit Window (± n Days)	14	14		
Concomitant Medications	X	X		Assess for change in concomitant medications (see Section 7.7)
UC Medications	X	X		
Tobacco / e-cigarette vape use	X	X		Assess for change in use
Physical Examination				See Section 9.5.1 for details
Weight	X	X		
Vital Signs (HR, BP, Temperature [°C])	X	X		
Complete Physical Examination	X			
Interim Physical Examination		X		
Electronic Diary (eCOA)				
Site Review of Electronic Daily Diary Compliance	X	X	X	
Blood and Urine Tests^c				See Section 9.5.4 for details
CBC and Differential Count	X		X	
Biochemistry ^d	X		X	

Table 2-2: Schedule of Activities for Year 2 (IM047029)

Procedure	Week 104 EOT/ET ^a (Day 728)	Week 116 PTFU (Day 812)	Unscheduled ^b	Notes
Visit Window (± n Days)	14	14		
Additional Efficacy Assessments^e				
PGA Collection	X	X		Physician-reported
RB Subscore	X	X		
SF Subscore	X	X		Recorded for 7 days prior to each study visit
HRQOL^f				
IBDQ	X	X		
Healthcare Resource Utilization^g				
AE Reporting				

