Monitor AEs	X	X	X	
Monitor SAEs	X	X	X	
COVID AEs	X	X	X	

Table 2-2: Schedule of Activities for Year 2 (IM047029)

Procedure	Week 104 EOT/ET ^a (Day 728)	Week 116 PTFU (Day 812)	Unscheduled ^b	Notes
Visit Window (± n Days)	14	14		
IP Supply				
Dispense IP			X	
Review Participant Compliance with IP	X		X	

AE, adverse event; ALT, alanine aminotransferase; AST, aspartate aminotransferase; BP, blood pressure; CBC, complete blood count; eCOA, electronic clinical outcome assessment; COVID, coronavirus disease; EDC, electronic data capture; [REDACTED] EOT, end of treatment; ET, early termination; [REDACTED] HR, heart rate; HRQOL, health-related quality of life; [REDACTED] IBDQ, Inflammatory Bowel Disease Questionnaire; INR, international normalized ratio; IP, investigational product; PGA, Physician's Global Assessment; PTFU, post-treatment follow-up; RB, rectal bleeding; [REDACTED] SAE, serious adverse event; SF, stool frequency; [REDACTED] UC, ulcerative colitis; [REDACTED] ULN, upper limit of normal; [REDACTED]

^a For participants who prematurely discontinue from the study, if possible, the EOT visit and follow-up visit should be conducted so that data can be collected at the time of study discontinuation and follow-up and for any further evaluations that need to be completed.

^b If required, an unscheduled visit can be planned anytime during the treatment period. Data regarding study procedures conducted at such unscheduled visits (eg, blood, stool, and urine tests; safety assessments) will be documented in the EDC tool.

^c Complete list of clinical safety laboratory assessments is provided in [Section 9.5.4](#).

^d Per physician discretion, INR may be collected if ALT or AST > 3 × ULN.

^e A brief description about additional efficacy assessments is provided in [Sections 9.1](#).

^f A brief description about HRQOL assessments is provided in [Section 9.1.2.2](#).

^g A brief description about healthcare resource utilization assessments is provided in [Section 9.10](#).

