8 DISCONTINUATION CRITERIA

8.1 Discontinuation From Study Intervention

Participants MUST discontinue IP for any of the following reasons:

- Participant's or investigator's request to stop study intervention. Participants who request to discontinue study intervention will remain in the study and must continue to be followed for the protocol-specified follow-up procedures. The only exception to this is when a participant specifically withdraws consent for any further contact with him/her or persons previously authorized by the participant to provide this information.
- Any clinical AE, laboratory abnormality, intercurrent illness, or other appropriate reason(s), which, in the opinion of the investigator, indicates that continued administration of study intervention is not in the best interest of the participant.
- Termination of the study by BMS.
- Loss of ability to freely provide consent through imprisonment or involuntarily incarceration for treatment of either a psychiatric or physical (eg, infectious disease) illness. (Note: Under specific circumstances and only in countries where local regulations permit, a participant who has been imprisoned may be permitted to continue as a participant. Strict conditions apply, and BMS approval is required.)

- Pregnancy (refer to [Section 9.2.5](#)).
- Significant non-compliance with the protocol (eg, procedures, assessments, medications). The investigator should discuss such issues with the Medical Monitor.
- Participant meets one of the following criteria for laboratory abnormalities in 2 sequential laboratory measurements taken up to 14 days apart:
 - Hb < 7.0 g/dL or a decrease of >30% from baseline
 - Lymphocyte count < $0.2 \times 10^9/\text{L}$ ($< 200/\text{mm}^3$) – see [Section 9.2.6](#) for temporary discontinuation guidance.
- Participant meets any of the following criteria for liver-related laboratory abnormalities. If these abnormalities are identified, repeat testing should occur within 48 to 72 hours, and these results should be discussed with the BMS Medical Monitor or designee. Additional recommendations on the recognition and investigation of potential drug-induced liver injury (DILI) are given in [Section 9.2.7](#).
 - ALT or AST > $8 \times \text{ULN}$ on a single occasion.
 - ALT or AST > $5 \times \text{ULN}$ for more than 2 weeks.
 - ALT or AST > $3 \times \text{ULN}$ and total bilirubin > $2 \times \text{ULN}$ or international normalized ratio (INR) > 1.5.

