 - ALT or AST > $3 \times \text{ULN}$ with the appearance of fatigue, nausea, vomiting, right upper quadrant pain or tenderness, fever, rash, and/or eosinophilia (> 5%).

Refer to the SOA for the data that will be collected at the time of treatment discontinuation and follow-up and for any further evaluations that can be completed.

All participants who discontinue study intervention should comply with the protocol-specified follow-up procedures, as outlined in [Section 2](#). The only exception to this requirement is when a participant withdraws consent for all study procedures, including post-treatment study follow-up, or loses the ability to consent freely (eg, is imprisoned or involuntarily incarcerated for the treatment of either a psychiatric or physical illness).

If study intervention is discontinued prior to the participant's completion of the study, the reason for the discontinuation must be documented in the participant's medical records, per local regulatory requirements in each region/country, as applicable, and entered on the appropriate eCRF page.

8.1.1 *Treatment Interruption*

Participants should be instructed that if they forget to take a dose, they can take it within 4 hours of the normal dosing time; otherwise, they should take their next dose at the regular time on the following day. If the participant vomits the dose, he/she should be instructed not to take another dose on the same day, but to take the next dose at the regular time on the following day. Participants will record whether they took the daily dose of medication in an electronic diary that will be reviewed periodically by the site staff and the site monitor.

If a dose is missed during the first 2 weeks of treatment, re-initiate treatment using dose escalation regimen. If a dose of study intervention is missed after the first 2 weeks of treatment, continue with the treatment as planned. If more than 7 consecutive days between Day 15 and Day 28 of treatment, or more than 14 consecutive days after Day 28 of treatment, re-initiate treatment using the dose escalation regimen. The Medical Monitor should be contacted to discuss completing the dose escalation schedule.

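### A cheap safety improvement: no pregnancy test is scheduled after Day 1, although pregnancy is a mandatory reason to stop drug throughout about 727 days of dosing

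*Combined protocol and SAP*

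**What the plan says.** - **Protocol Section 2, Table 2-1.** The row "Pregnancy Test - Serum or Urine beta-hCG" is marked at Screening and Day 1. The cells for Weeks 4, 12, 26, 52 and Unscheduled are blank. Footnote e concerns only the test before dosing: "Pregnancy test anytime within 7 days prior to day of study intervention initiation is permissible".
- **Section 2, Table 2-2.** No pregnancy row is visible for Week 104, Week 116 or Unscheduled. The blood and urine block lists CBC and biochemistry only.
- **Section 9.5.4, Table 9.5.4-1.** The pregnancy test is labelled as a screening test. A separate urine beta-hCG line for WOCBP has no time point.
- **Section 3.3.1, Table 3.3.1-1.** Fetal risk is listed, with rationale and mitigation deferred to the product label.
- **Section 8.1.** Pregnancy is in the list introduced by "Participants MUST discontinue IP for any of the following reasons".
- **Section 9.2.5.** A pregnancy must be reported within 24 hours of the site becoming aware of it.
- **Section 6.1, criterion 7a(v)(2).** WOCBP must use contraception with a failure rate below 1% per year during treatment and for at least 90 days.
- **Appendix 4.** WOCBP who choose abstinence are to go on having the pregnancy tests set out in Section 2. The appendix describes itself as general text suited to most trials.
- **Dispensing (Table 2-1).** Drug is handed out at Weeks 4, 12, 26 and 52 and at unscheduled visits.

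**The concern.** A mandatory stopping rule works only once someone knows that its condition has been met. The haemoglobin, lymphocyte and ALT/AST rules in Section 8.1 are fed by CBC and biochemistry at every on-treatment visit and in both Unscheduled columns. Pregnancy has the same mandatory status, but no scheduled procedure would reveal it. Followed as written, the schedule lets a WOCBP be given drug at Week 52 and continue to Day 728 with no test since Day 1. The 24-hour reporting clock does not help, because it starts at awareness. Appendix 4 also refers to continuing tests in Section 2, where none exists on treatment.

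What is at stake is avoidable fetal exposure in a small number of participants. The primary endpoints are not involved.

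**Working it through.** **Inputs from the protocol.** Visit days 1, 28, 84, 182, 365 and 728 (Tables 2-1 and 2-2); 150 + 100 = 250 treated participants (Section 10.2); contraceptive failure below 1% per year (Section 6.1).

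**Assumptions, not in the protocol.** WOCBP are 20% to 40% of those treated; all complete dosing; urine test specificity is 99.9% to 99%.

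**1. Plan's own figure.** 104 × 7 = 728, which matches the stated Day 728 for Week 104. Dosing time is 728 − 1 = 727 days, or 727/365.25 = 1.99 years.

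**2. Scheduled checks behind the stopping rules.**

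| Test | On-treatment visits | Unscheduled columns |
|---|---|---|
| CBC, biochemistry | 5 of 5 | 2 of 2 |
| Pregnancy | 0 of 5 | 0 of 2 |

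**3. Intervals.** With tests at the existing visits the gaps are 27, 56, 98, 183 and 363 days, which sum to 727.
- Longest stretch without a test: 727 days now, 363 with the change.
- Up to Week 52: 365 − 1 = 364 days now, 183 with the change.
- Week 52 to Week 104: 363 days either way, or 335 to 391 with a 14-day window at each end. That is 363/727 = 49.9% of dosing time.

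**4. Expected pregnancies.** WOCBP: 0.20 × 250 = 50 to 0.40 × 250 = 100. At the 1% ceiling, 50 × 1.99 × 0.01 = 1.0 and 100 × 1.99 × 0.01 = 2.0. Before Week 52, multiply by 364/727 = 0.50, which gives 0.5 to 1.0.

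**5. Burden.** Five tests each: 250 to 500 tests. False positives: 250 × 0.001 = 0.25 to 500 × 0.01 = 5. For Weeks 4 to 52 alone there are 200 to 400 tests and 0.2 to 4 false positives.

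**6. Does a short hold do harm?** Section 8.1.1 requires re-titration after an interruption of "more than 7 consecutive days between Day 15 and Day 28 of treatment, or more than 14 consecutive days after Day 28 of treatment". A hold of at most 7 days stays within both limits. The Week 4 visit can fall on Day 21 at the earliest (28 − 7), so no hold at a scheduled visit reaches the first two weeks, when any missed dose restarts titration. An unscheduled test before Day 15 could. Section 10.3 makes participants non-responders if they discontinue drug before the primary visit, so the hold must be recorded as an interruption.

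**The case against.** The case for leaving the schedule alone has real strength.

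- **It looks deliberate.** Table 9.5.4-1 restricts the test to screening. Fetal-risk mitigation is left to the product label, which is not among the documents. Both points stand. They mean the schedule may follow a considered choice, and that label compliance cannot be judged here.
- **Other mandatory stops are symptom-driven too.** Confirmed macular edema requires stopping drug, yet the fundus examination is scheduled only at screening. This weakens the comparison with CBC and biochemistry. It does not remove the practical difference that a urine test fits easily into an existing visit.
- **Controls already exist.** There is counselling, required contraception, exclusion of women planning pregnancy, and a physical examination at every on-treatment visit. Testing on suspicion is also possible: "If required, an unscheduled visit can be planned anytime during the treatment period". These reduce the benefit but do not bring it to zero. Appendix 4 itself notes that typical-use failure rates may differ from those under consistent, correct use.
- **False positives may outnumber useful detections.** Through Week 52 the ranges are 0.2 to 4 false positives against 0.5 to 1.0 pregnancies, some of which would be noticed anyway. This is a fair point, and it is why the hold must be short and handled as set out under the fix.
- **A redacted row is possible.** The Table 2-2 legend has no beta-hCG entry (it runs "AST, aspartate aminotransferase; BP, blood pressure; CBC, complete blood count"), but legends here are not reliable row lists: the Table 2-1 legend defines terms that no visible row uses. The healthcare resource utilization heading also stands empty in both tables. Table 9.5.4-1 is better support for reading the schedule as it appears, though not proof.

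A reader might infer from Appendix 4 that on-treatment testing was intended and dropped by mistake. The documents do not support that. The appendix is general text, and its reference shows a loose end rather than a lost schedule.

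**Conclusion.** The point holds as a low-cost safety suggestion. In the visible schedule, pregnancy tests are planned at 0 of 5 on-treatment visits, while fetal risk is listed, pregnancy requires stopping drug, and dosing lasts about 727 days.

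The gain is modest: at most about 1 to 2 pregnancies over the study, half of them before Week 52, under the assumed 50 to 100 WOCBP and full exposure at 1% per year. At Weeks 4, 12, 26 and 52 a positive result could shorten exposure. At Week 104 it can only document it.

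Two stronger readings should be resisted. One is that pregnancies would go undetected: self-report, AE questioning, examination and unscheduled testing all remain. The other is that efficacy results are compromised: nothing here touches the response rates or their confidence intervals.

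**What to change.** At the next amendment:

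1. In Tables 2-1 and 2-2, add a beta-hCG test for WOCBP before dispensing at Weeks 4, 12, 26 and 52, at Week 104 to document exposure, and in both Unscheduled columns (at any dispensing, or on suspicion). Urine on site is simplest where a same-visit result is wanted; serum from blood already being drawn is the alternative.
2. In Table 9.5.4-1, change the timing from screening to per SOA. Otherwise it would conflict with the new schedule. The Appendix 4 reference then has on-treatment tests to point to.
3. Add a footnote: a positive urine test holds drug for at most 7 days pending a serum result. The hold is recorded as an interruption under Section 8.1.1, not as a discontinuation. If serum is positive, Sections 8.1 and 9.2.5 apply.

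**Cost.** Marks in one existing row, one new row, one edited table entry and one footnote. About 5 tests per completing WOCBP, or 250 to 500 in all under the assumptions, plus any at unscheduled visits. Each of the roughly 0.25 to 5 false positives costs a serum test, a short hold and possibly an AE entry under Section 9.2.6. No new visit is needed. The 363-day Year 2 gap stays unless an unscheduled visit falls within it.

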- Malignancy: Participants should be carefully monitored for malignancies (including dermatologic malignancy). The investigator will complete dermatological examinations to monitor the potential development of new cutaneous malignancies during the study. Participants with any suspicious finding noted during the examination will be referred to an appropriately qualified dermatologist for evaluation and treatment, if warranted.
- Serious or opportunistic infection: Tuberculosis, serious bacterial infections, systemic fungal infections, viral infections, such as herpes infections (including herpes zoster and disseminated herpes simplex), and protozoan infections will be considered AEIs.
- Pulmonary effects: If a participant discontinues due to a respiratory AE, the investigator should ensure that the participant has had adequate evaluations, as clinically indicated by a pulmonologist (consider pulmonary function tests, chest X-ray, or high-resolution computed tomography, based on findings of the other examinations), at the time of the AE.
- Hepatic effects: If participants have elevations in liver function tests (LFTs; ALT or/and AST) $\geq 3 \times$ ULN, a retest should be performed as soon as possible but no later than 14 days after the original test. Upon confirmation of the abnormality, retests should be performed weekly until the elevated LFT decreases to below $3 \times$ ULN. At any time, if any of the following occur and there are no apparent alternative causes for the finding, the study intervention must be permanently discontinued:
 - ALT or AST $> 8 \times$ ULN or
 - ALT or AST $> 5 \times$ ULN with confirmation within 2 weeks or
 - ALT or AST $> 3 \times$ ULN and (total bilirubin $> 2 \times$ ULN or INR > 1.5) or
 - ALT or AST $> 3 \times$ ULN with the appearance of fatigue, nausea, vomiting, right upper quadrant pain or tenderness, fever, rash, and/or eosinophilia ($> 5\%$).
- The investigator should establish causality.
- After discontinuation due to elevation of ALT or AST $> 5 \times$ ULN or concurrent elevations of ALT or AST $> 3 \times$ ULN and bilirubin $> 2 \times$ ULN, further liver function evaluations should be performed (for example, coagulation panel and alkaline phosphatase) in consultation with the Medical Monitor.

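### INR > 1.5 with ALT/AST > 3 × ULN is a mandatory stop, but the only readable text naming INR for collection leaves the test to physician discretion at that same threshold

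*Combined protocol and SAP*

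**What the plan says.** Section 8.1 lists four liver criteria among the reasons for which study drug has to be stopped. One combines ALT or AST > 3 × ULN with total bilirubin > 2 × ULN "or international normalized ratio (INR) > 1.5". Section 9.2.1.1 repeats the criterion. Its brackets make clear that INR is an alternative to bilirubin, and that either one, added to the enzyme rise, is enough. The stop there is conditional: "if any of the following occur and there are no apparent alternative causes for the finding, the study intervention must be permanently discontinued".

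On measurement, the Biochemistry row of Table 2-2 carries footnote d, which says "Per physician discretion, INR may be collected if ALT or AST" is above 3 × ULN. The Biochemistry row of Table 2-1 (Year 1) carries a footnote that only refers the reader to Section 9.5.4. The readable rows of Table 9.5.4-1 include ALT, AST, total and direct bilirubin and the leukocyte differential, but no INR or other coagulation test.

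The retest rule in Section 9.2.1.1 concerns "elevations in liver function tests (LFTs; ALT or/and AST") of at least 3 × ULN. It asks that "a retest should be performed as soon as possible but no later than 14 days after the original test" and, once the rise is confirmed, that "retests should be performed weekly until the elevated LFT decreases to below" 3 × ULN.

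**The concern.** A mandatory stopping rule works only if the quantity that it depends on is measured. Here the enzyme threshold that opens the rule is also the threshold at which footnote d makes INR optional. The enzyme and bilirubin parts can be checked from the routine panel. The INR part can be checked only if someone chooses to order the test.

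What is at stake is participant safety in a narrow case: a participant with ALT or AST above 3 but not above 5 × ULN, bilirubin not above 2 × ULN, none of the symptoms in the fourth criterion, eosinophils not above 5%, no apparent alternative cause, and INR > 1.5. This participant has to stop. A site that follows the readable text can repeat ALT and AST weekly and continue dosing without learning that the rule is met.

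**Working it through.** The plan gives no figure on this point to reproduce. The check compares the rule with every readable provision that might supply the INR value.

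1. **The rule.** INR appears in 1 of the 4 liver criteria in Section 8.1, as one of its 2 alternatives. The gap is confined to that limb.

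2. **Table 2-2 footnote d.** It names INR at the right threshold, but as an option.

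3. **Table 2-1 and Table 9.5.4-1.** No readable requirement. Both carry redactions.

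4. **Repeat testing in Section 8.1.** "If these abnormalities are identified, repeat testing should occur within 48 to 72 hours". This starts only once a listed criterion has been recognised. For the INR limb, INR would already have to be known, so the repeat cannot reveal an unrecognised case.

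5. **Retests in Section 9.2.1.1.** These follow ALT and AST. INR is not named.

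6. **Coagulation panel in Section 9.2.1.1.** It is given as an example of work-up after discontinuation, for ALT/AST > 5 × ULN or > 3 × ULN with bilirubin > 2 × ULN. It comes after the decision that INR should inform, and the INR-only case does not trigger it.

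7. **Potential DILI, Section 9.2.7.** The definition needs bilirubin > 2 × ULN, so it also misses the INR-only case.

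8. **The symptom criterion in Section 8.1.** It stops participants above 3 × ULN "with the appearance of fatigue, nausea, vomiting, right upper quadrant pain or tenderness, fever, rash, and/or eosinophilia" (> 5%). It catches cases with those features and does not depend on INR.

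Mandatory INR measurements at ALT/AST > 3 × ULN in readable text: 0.

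**Size, under stated assumptions.** The documents give no rate of ALT/AST > 3 × ULN and no rate of raised INR among those who cross it. Treated participants: 150 + 100 = 250.

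- Crossing 3 × ULN, assumed 1% to 5%: 0.01 × 250 = 2.5; 0.05 × 250 = 12.5, so about 3 to 13.
- INR > 1.5 as the only stop condition met, assumed 0% to 10% of those: lower bound 0; upper bound 0.10 × 12.5 = 1.25, so 0 to about 1.

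The first range is the number who would be tested. The second is the number for whom the gap could change the decision.

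**The case against.** The strongest reply is that the sponsor considered INR at exactly this threshold and chose discretion. On that view the INR limb adds a stop when the value happens to be known, and the protection comes from elsewhere: bilirubin and the differential are in the routine panel, the investigator has to stop for any laboratory abnormality judged to make continuing unwise (Section 8.1), immediate safety concerns go to the Sponsor (Section 9), and persisting ALT/AST > 2 × ULN is excluded at entry (Section 6.2). These safeguards do reduce the risk, and they are why the point is minor. None of them requires the INR that would show the rule is met, and Section 8.1 does not limit the criterion to participants whose INR happens to be available.

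The second reply concerns lost text, and it largely stands. A reader might infer that the protocol has no INR requirement at all in Year 1. The documents do not support that as fact. Table 2-1 and Table 9.5.4-1 are partly redacted, the legend of Table 2-1 defines LFT without a readable use, and one of its footnotes (h, on the *C. difficile* row) is not readable. The abbreviation list of Table 2-1 omits INR while that of Table 2-2 defines it. This counts weakly against a hidden entry but settles nothing, since the same list omits IP, which the table uses. Table 3.3.1-1 also refers liver-injury mitigation to the product label, which is not available here.

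A reader might also infer that footnote d confines INR to Year 2. That is arguable at best. The table is titled Year 2, but its EOT/ET column serves participants who leave early at any time, and its unscheduled visits may fall anywhere in the treatment period. On either reading INR remains optional.

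**Conclusion.** The inconsistency is real on the readable text: a mandatory stop depends on a test that the only readable collection provision makes optional at the rule's own enzyme threshold. The INR limb can go unchecked while dosing continues. Footnote d is itself readable, so this part of the finding does not depend on what is redacted. The Year 1 part does.

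It would be too strong to conclude that participants who meet the stop will generally be missed. The number affected is unknown, probably very small and possibly zero. The range of 0 to about 1 of 250 rests wholly on the assumed 1% to 5% and 0% to 10%. This is a minor safety alignment, worth making because it is cheap. It has no bearing on the primary endpoints' definition or precision.

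**What to change.** 1. Reword Table 2-2 footnote d so that INR must be collected if ALT or AST exceeds 3 × ULN.
2. In Section 9.2.1.1, require INR at the first confirmatory retest, repeated at later weekly retests only if ALT/AST rises or the investigator judges it necessary.
3. Unless redacted text already does so, put the same note on the Biochemistry row of Table 2-1 and list the triggered INR in Table 9.5.4-1.

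If the sponsor considers INR unnecessary at this threshold, the consistent alternative is to remove it from the mandatory criterion.

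**Cost.** Wording in up to four places, and one routine blood test per participant crossing 3 × ULN, drawn with a retest that is already planned. Under the assumed 1% to 5%, that is 2.5 to 12.5 first tests. If half of those crossing needed 1 to 3 repeats (also an assumption), repeats would add 1.25 × 1 = 1.25 to 6.25 × 3 = 18.75. The total is 3.75 to 31.25, or about 4 to 31 INR tests over the whole study.
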